## **10) Data Analysis Plan**

Retrospective data analysis will be conducted by the research team with data collected from the electronic medical record as well as the checklists (oxygen saturation, demographics, proning protocol) for both the interventional and control group. See attached documents for consent/proning protocol documents.

This study will be a randomized controlled trial. The primary outcome will be time (days) until discharge from the acute care unit to home or lower level of care (e.g., long-term care), and the primary hypothesis test will compare time-to-discharge between "prone" and "not prone" treatment arms.

A sample size of 48 patients per group (N=96) will provide 80% power to detect a 50% decline in time-to-discharge using a log-rank test.

## **11) Withdrawal of Subjects**

The researchers do not anticipate circumstances in which the subjects will be withdrawn from the research study without their consent. Patients who otherwise withdraw from the study will be censored on the withdrawal day with the following process: If the patient started the study and then wished to have their data removed, the patient would communicate that to the nurse assigned, who would then call the principal investigator (number provided to the unit). The investigator would then delete the profile from REDCap and remove the medical record number from the study records.

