##### **Exclusion Criteria:**

The exclusion criteria included those that are not COVID 19 positive. Those patients that are COVID -19 positive and in an ICU setting, or in need of ICU level respiratory treatments and interventions would be excluded, as well as those with respiratory distress (defined as immediate need for intubation, respiratory rate over 35, PaCO2 level above 65, and accessory muscle use) or in hemodynamic instability (systolic blood pressure below 90) or arrhythmia. The researchers would also exclude patients that have agitation or who have altered mental status, unstable spine/thoracic injury or recent abdominal surgery, significant pressure ulcers (above stage 1), pregnant patients past the 2nd trimester, and patients that have concerning neurological issues (such as seizures). Patients that are unable to change positions independently will also be excluded.

*Describe how individuals will be screened for eligibility.*

This is a single-center prospective study which will be conducted over a period of 8 months on a telemetry-monitored, acute care unit in a large tertiary teaching hospital in Houston, Texas. Randomized sampling will be used to recruit and consent 96 patients that meet the study inclusion criteria (48 in the intervention group and 48 in the control group). This study will seek approval from the Common Spirit Health Institutional Review Board, and all participants receiving the intervention will be consented (see consent form attached).

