## **8) Procedures Involved**

**Study Design:** This will be a prospective randomized cohort study in which data will be collected for over 14 days or until discharged or transferred to a lower level of care from the telemetry-monitored, acute care unit. Data collected on study participants will include the need for escalating respiratory care as well as length of stay in the acute care unit. Comparative analysis will be conducted with retrospective data collected from hospitalized patients (the control group) with a diagnosis of COVID-19 on a non-ICU acute care, telemetry-monitored unit that meets the hypoxemia criteria, but that will not receive the proning intervention. The data from the control group will be collected by a retrospective chart analysis after 14 days past their discharge date.

On a confirmed COVID-19 non-ICU acute care, telemetry-monitored unit, there will be two sets of patients: patients that will receive the intervention of proning plus standard of care, and patients that receive standard of care, but not the proning intervention. Confirmed COVID-19 positive patients are randomly assigned by bed control to a room upon admission to the unit. Patients will be randomized upon admission to the acute care, telemetry-monitored unit, and selected based

on inclusion criteria. The patients that will be prone will be identified by a door slot "slider" that is purple. Timing devices will be purchased and placed at the nurses' station, and checklists to indicate proning times will be placed inside the room with a patient identification sticker. The researchers will be following the proning protocol for acute care patients provided by CommonSpirit Health (CSH).

Patients will consent to participation (using an approved consent document from the CSH IRB), and an order for the proning protocol will be entered in the EMR by the physician. The patient will be educated about self-proning, and instructed to self-prone every 2 hours. The nursing staff will document patient position on the checklists every 2 hours.

1. Upon initiation of the initial proning, the patient will be monitored by the RN for adverse effects for 15 minutes (such as inability to tolerate position or signs of respiratory distress).

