2. If the patient tolerates the proning well, the procedure can continue and the RN will set the timer for 2 hours, enter the patient's oxygen saturation into the EMR, and document the position (prone or supine) on the checklist. O2 saturation will be documented at least every 4 hours per unit protocol.
3. The 2 hour timer will be reset each set of 2 hours by the nursing staff, and the intervention will continue until the end of the study period or until the patient is discharged or transferred from that unit.
4. The checklists will be placed in a binder at the nurses' station at the end of each shift and collected daily by a member of the research team.
5. This intervention for each "proned" patient will continue until either of the following occur: either the patient is discharged or transferred to a lower level of care from the acute care floor, or 14 days have passed.
6. A retrospective chart review will be completed by the research team to ascertain length of stay on the acute care, telemetry monitored unit, as well as the need for escalation of respiratory care. Escalation is defined by a need for oxygen requirements above 6 liters of oxygen on the nasal cannula.

*If the patient is assigned to the control group, that patient will receive the standard of care treatment designated by BSLMC policy per their condition on the COVID-19, acute care, telemetry-monitored unit.*

**Data Analysis:** Retrospective data analysis will be conducted by the research team with data collected from the electronic medical record as well as the checklists (oxygen saturation, demographics, proning protocol) for both the interventional and control group. See attached documents for consent/proning protocol documents.

This study will be a prospective cohort study in which data will be collected on subjects for the designated time period. Data will be collected from the electronic medical record as well as the checklists. Data collection will include basic patient demographics, specifically age and gender, height, weight and ethnicity. Clinical data to be collected include O2 saturation, respiratory support methods, proning duration/compliance, presence of hospital acquired pressure injuries,

and need to escalate care to ICU, including initiation of mechanical ventilation. The same data will be collected for the control group - except for proning duration/compliance as they will not receive this intervention.

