## **12) Risks to Subjects**

The researchers foresee minimal risks in this study to the participant. Possible risks include:

- Inability to maintain the prone position, possibly resulting in O2 desaturation and other negative respiratory effects, such as intubation
- Skin breakdown
- Patient discomfort in turning every 2 hours/patient inconvenience for documentation, especially overnight

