### ***Waiver or Alteration of the Consent Process***

For our patients assigned to the control group, a waiver of consent will be requested.

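### Section 11 censors every withdrawing patient without separating stopping proning from refusing chart use; since only proned patients can withdraw, this can bias the log-rank test in a direction the protocol does not settle

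*Protocol*

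**What the plan says.** Section 11 (Withdrawal of Subjects) gives one rule for all voluntary withdrawals: "Patients who otherwise withdraw from the study will be censored on the withdrawal day". The sentence then describes a process for a narrower group. "If the patient started the study and then wished to have their data removed", the nurse calls the principal investigator, and "The investigator would then delete the profile from REDCap and remove the medical record number from the study records".

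The arms differ in who can withdraw. Section 4, under the exclusion criteria, says that "all participants receiving the intervention will be consented". Section 18 adds: "For our patients assigned to the control group, a waiver of consent will be requested". Section 8 says of controls: "The data from the control group will be collected by a retrospective chart analysis after 14 days past their discharge date".

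The primary outcome in Section 10 is days until discharge from the acute care unit, compared between arms by a log-rank test. Section 8, step 6, gives the source of the stay: "A retrospective chart review will be completed by the research team to ascertain length of stay on the acute care, telemetry monitored unit". Sections 8 and 9 also collect proning duration and compliance as a separate item.

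**The concern.** A log-rank test treats a censored patient as having the same future discharge rate as the patients in that arm who remain. If those who withdraw would have stayed longer or shorter than the rest, that fails. Here it can fail in one arm only: controls are unconsented charts with no practical route to withdraw, so nothing comparable happens on their side to offset it.

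Much of this censoring may also be avoidable. A patient who stops turning but does not object to chart use still has a discharge date in the record from which the study reads length of stay. Because Section 11 does not define withdrawal, staff could reasonably log such a patient as withdrawn. Non-adherence within the assigned arm would then become removal from the risk set of the primary test.

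**Working it through.** **Inputs from the protocol.** 48 patients per arm, log-rank test, 80% power for a 50% decline in time to discharge (Section 10); 14-day limit on the intervention (Section 8). Alpha, control median, expected withdrawals and reasons for withdrawal are not given.

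**The plan's own figure.** Read a 50% decline as a rate ratio of 2 (exponential times) and assume two-sided 5%.

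- Schoenfeld: 4 × (1.960 + 0.842)² / (ln 2)² = 4 × 7.85 / 0.480, which gives 66 events.
- Freedman: 7.85 × ((2 + 1)/(2 − 1))² = 7.85 × 9, which gives 71 events.

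N = 96 then needs 69% (66/96) to 74% (71/96) of patients with an observed discharge. That is plausible but cannot be confirmed, and no withdrawal allowance can be recovered from it.

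**Size by hand if only sicker patients leave.** Let a share p of each arm have stays k times longer, with no true effect. If that share is censored early from the proned arm only, the apparent starting rate ratio is 1 / (1 − p + p/k).

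- p = 10%, k = 2: 1/0.950 = 1.05
- p = 20%, k = 3: 1/0.867 = 1.15
- p = 25%, k = 3: 1/0.833 = 1.20

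If withdrawal is unrelated to stay, k = 1 and the ratio is 1. If quicker patients leave, k is below 1 and so is the ratio.

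**Simulation 1, sicker proned patients only.** No true effect, 48 per arm, 8-day median in the other patients, 14-day cap, withdrawal uniform over days 0-3. False benefit is Z > 1.96, nominally 2.5%. Rate ratios are from 3,000 trials per setting; false-benefit rates are from a repeat with 8,000.

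| Withdrawing (stay) | Rate ratio | False benefit |
|---|---|---|
| 10% (2×) | 1.06 | 3.8% |
| 15% (2×) | 1.08 | 5.7% |
| 15% (3×) | 1.13 | 6.7% |
| 20% (3×) | 1.18 | 9.5% |
| 25% (3×) | 1.22 | 11.6% |

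A separate run over this range gave 4.7% to 12.8%. With only about half of withdrawals related to prognosis, the ratio was 1.05-1.09 and false benefit 3.9-5.7%. Following the same patients to discharge or day 14 gave ratios near 1.00 and about 2-3%.

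**Simulation 2, all three directions.** No true effect, 48 per arm, 7-day baseline median, half of patients at 0.5 and half at 1.5 times the baseline discharge rate, withdrawal in days 0-3 of the proned arm, 1,500 trials. Mean log-rank Z, positive favouring proning:

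| Censored on withdrawal; who leaves | 10% | 20% | 30% |
|---|---|---|---|
| Unrelated to prognosis | +0.01 | −0.01 | −0.01 |
| Sicker only | +0.14 | +0.40 | +0.73 |
| Healthier only | −0.16 | −0.38 | −0.64 |

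At 30%, false benefit is 11.4% if sicker patients leave and 0.4% if healthier ones do; in the latter case false harm is 9.9%. Chart follow-up of everyone gave a mean Z between −0.02 and +0.05 in all nine settings, against a Monte Carlo standard error of 1/√1500 = 0.026.

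**If the deletion half of the sentence operates instead.** With withdrawal unrelated to prognosis, mean Z was +0.10, +0.15 and +0.25 at 10, 20 and 30%. Only patients not yet discharged can be deleted, so deletion removes longer stays even then.

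**The case against.** The strongest reply is that Section 11 may not reach the patients at issue. The only process it describes is for someone who wants the data removed, and compliance is recorded separately, so a patient who merely stops proning may never be treated as withdrawn. For someone who refuses record use, censoring on that day is proper. The date being in the chart does not help, because the study may no longer use it. All of that stands for those who refuse record use. It does not rescue the general clause, which covers everyone who withdraws and draws no line between the two groups.

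A reader might infer something stronger: that the rule by itself biases the test toward proning. The documents do not support that. One-armed censoring alone produces no bias, and the sign reverses if healthier patients leave. Section 12 lists risks, not reasons for withdrawal. Its first item, inability to hold the position with possible desaturation, suggests a worse course. But "Patient discomfort in turning every 2 hours/patient inconvenience for documentation, especially overnight" has no stated link to severity, and an improving patient might equally tire of being turned at night. Simulation 1 builds in its direction by letting only sicker patients leave, so it shows what could happen, not what to expect.

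**Conclusion.** The point holds as a fixable weakness in the withdrawal rule. Section 11 censors all withdrawals without distinguishing stopping proning from refusing chart use, and withdrawal is in practice confined to the proned arm (provided the control waiver is granted). The primary test can therefore be biased, with unknown size and direction.

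The range of about 4-5% to 12-13% false benefit applies only if sicker proned patients alone withdraw, early, at 10-25% of the arm (roughly 5 to 12 of 48) with stays 2-3 times longer. Those figures, the 8-day median and the 2.5% nominal level are assumptions. The case for change does not depend on the direction, because chart follow-up kept the test close to its nominal level whichever patients left.

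The contradiction within the sentence is firm and needs no assumption: a patient whose profile has been deleted cannot be censored.

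**What to change.** Reword Section 11 so that:

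- a patient who stops proning or other study procedures but does not refuse chart use stays in the assigned arm and is followed by chart review to discharge or day 14, without censoring;
- only a patient who refuses further use of the record is censored, on the day of refusal;
- the deletion instruction is reconciled with this, stating what is kept when a patient asks for removal and whether that patient enters the analysis as censored or not at all.

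Offer the two options separately in the consent form, and report the number choosing each. The cost is wording in Section 11, the matching text in Section 9 and the consent form. No new data are needed, because length of stay is already abstracted from the chart.

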## **12) Risks to Subjects**

The researchers foresee minimal risks in this study to the participant. Possible risks include:

- Inability to maintain the prone position, possibly resulting in O2 desaturation and other negative respiratory effects, such as intubation
- Skin breakdown
- Patient discomfort in turning every 2 hours/patient inconvenience for documentation, especially overnight

## **13) Potential Benefits to Subjects**

The researchers foresee benefits to the patient for being involved in the study. These benefits should last for at least the length of the data collection on the patient. The benefits include:

- Shorter time to discharge or transfer to lower level of care (measured in days)
- Decreased need for O2 supplementation; higher O2 saturations recorded

## **14) Setting**

The research study will be conducted in St. Luke's Health - Baylor St. Luke's Medical Center - Houston, TX (address: [name]), in a telemetry-monitored, acute care unit for covid-positive patients. The researchers will consent randomly assigned patients from that unit, and the intervention will be contained to that unit.

The study is being propagated by BSLMC's Nursing Research and Education Council after having been approved by the CNO, and is being submitted for review by the CSH Institutional Review Board. After approval, the study will be commenced.

## **15) Resources Available**

The members of the research team are [name], [name], [name], [name], [name], and [name].

All team members involved in the study are registered nurses (RNs) with bedside experience in an acute-care facility that provides high acuity patient care. The aforementioned team members have completed CITI training specific to conducting research via IRB approval and oversight under institutional guidelines, policies, and ethics. The members of this research team will be conducting this research for the continuation of evidence based practice amidst the COVID-19 pandemic that will provide much needed guidance for the treatment of the COVID-19 affected population. Each member of the study promotes adequate knowledge of the local study hospital, culture and larger local community.

The feasibility of recruiting the required number of suitable subjects within the agreed recruitment period is to be determined once data collection commences and is currently unknown. This will be addressed knowing that the active COVID-19 population is declining due to increased vaccinations and compliance by the general public with adhering to social distancing and wearing personal protective equipment. Given this, the percentage of potential subjects needing to be recruited will be based on the number of qualified study participants. The researchers estimate that in order to obtain statistically significant results, the sample size will need to be 96 patients minimum, with a goal of 130, splitting evenly into control and intervention groups. The research team will have access to the unit's patients at time of data collection per the unit manager and approval of the facility for the estimated time of data collection.

The research study will take place on a COVID-19, acute care, telemetry-monitored unit.

Each member of the research team is expected to devote time to this research study daily during the data collection period for approximately a half an hour each day. This will entail education of the nursing staff affected and collection of both the electronic and paper records. That process is as follows:

- At the beginning of each day, staff huddles occur on the unit at approximately 6:45 AM. A member of the research team will be present at huddle daily to educate the staff nurses on the proning intervention.
- Once each intervention patient is confirmed via random assignment, the research team member assigned that day will meet with the nurse assigned to the

intervention patient. The research team member will obtain consent from the patient. That team member will assess if the nurse needs help monitoring the patient for the initial 15 minutes of proning, and assist as needed.

- That team member will also educate the nurse assigned as to how often proning occurs (every 2 hours), to document patient position on the checklist every two hours, the proning protocol, and where to put the checklist at the end of their shift. The team member will leave upon confirmation of correct implementation of the study.
- The checklists from the intervention patients will end up in a binder at the end of the shift, and the binder will be emptied at that time by a member of the research team. These checklists' data will be entered into the computer by the research team, kept until the end of data collection period in a locked filing cabinet, and then destroyed at the end of the data collection period.

The resources for the patient should there be more than minimal harm caused include the medical resources of our facility.

## **16) Confidentiality**

There are 2 sets of data to be protected during this study: electronic and paper sets of data. The paper data will be only transported by members of the research team from the point of collection and stored in locked filing cabinets. This data will be destroyed at the end of the data collection period - approximately 8 months. The electronic data will be physically entered by members of the research team directly from the electronic medical record to the REDCap software database after being coded with a REDCap generated personal ID. The list of personal IDs linked to the medical record numbers will be destroyed at the end of the data analysis period - approximately 8 months. The REDCAP software is a web-based application used to capture data and create databases in an encrypted environment that is user-protected and HIPAA compliant. This electronic data will only be accessed by members of the research team during working hours at the facility, on CHI protected servers managed and maintained by CHI Information Technology.

The researchers do not anticipate any necessary breaks in confidentiality for the duration of this study.

The risk of loss of confidentiality will be minimized by taking the following steps: (1) Data collected from study participants will be maintained in locked file cabinets, in password protected CHI servers managed and maintained by CHI Information Technology. (2) Subject names and other identifiers will be removed from study data and will be replaced by unique study numbers. (3) The documents connecting the subjects to their study numbers will be kept separately from subject data and in locked file cabinets, in password protected CHI servers managed and maintained by CHI IT. (4) Study personnel will be the only individuals with filing cabinet keys and computer passwords. Study personnel will only access this data while at work.

## **17) Provisions to Protect the Privacy Interests of Subject**

During the informed consent process, the patient will be given the opportunity to ask questions and disclose any discomfort with the study or study procedure, with both the research team member and the nurse assigned to the patient. The process of patient confidentiality within the study will be fully explained to the

patient, as specified above - the fact that the researchers will only have access to demographic information, and not personal identifiers outside of medical record numbers, and that the data will be encoded upon entry into the secure database. If the patient wishes to withdraw from the study at any time, that process will be explained.

